## Research Plan

- **Study Design**
  - Retrospective chart review
- **Setting for the study**
  - The retrospective chart review will be performed on TriHealth EPIC platform at one of the various clinical locations.
- **Participants**
  - Study population: All women 18 years of age or older, who underwent pelvic floor gynecologic surgery (for the indication of pelvic organ prolapse or stress urinary incontinence) performed by a physician at Cincinnati Urogynecology Associates, TriHealth Inc between April 2015 and September 2015, and April 2016 and September 2016, who required indwelling urinary catheter use upon discharge from the hospital.
  - A chart review will be performed on all patients who underwent pelvic floor gynecologic surgery performed by a physician at Cincinnati Urogynecology

Associates, TriHealth Inc between April 2015 and September 2015, and April 2016 and September 2016 to determine which patients required discharge with an indwelling urinary catheter.

- The charts of those patients who required catheterization postoperatively will be reviewed further and will make up our study population of interest.
- Inclusion criteria
  - Adults 18 years of age or older
  - Underwent pelvic floor gynecologic surgery (for the indication of pelvic organ prolapse or stress urinary incontinence) performed by a physician at Cincinnati Urogynecology Associates, TriHealth Inc between April 2015 and September 2015, and April 2016 and September 2016
  - Required indwelling urinary catheterization upon discharge from the hospital postoperatively
- Exclusion criteria
  - Intraoperative bladder injury, fistula repair, urethral diverticulectomy, or any other need for prolonged catheterization
  - Complications in the 2 weeks following surgery requiring reoperation and subsequent catheter use
  - Allergy to cranberry or its components
  - Failure to present for both the two-week and six-week postoperative office visit
- Sample size
  - Cranberry juice capsules were incorporated into the standard practice of Cincinnati Urogynecology Associates, TriHealth Inc in mid-March 2016. We plan to review six months of data from similar time frames of 2015 and 2016. This will allow us to capture a similar number of patients in the exposure (cranberry juice capsules, 2016) and no exposure (no cranberry juice capsules, 2015) groups.

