  - Given the fact that Cincinnati Urogynecology Associates, TriHealth Inc typically performs 400 surgeries annually, we estimate that reviewing a total of 12 months of data will result in accessing approximately 400 charts.

● **Data Collection**

- Independent variables: cranberry juice capsules prescribed as part of discharge medication regimen
- Dependent variables: UTI as defined by documentation of positive urine culture or treatment by an involved provider, with documentation in the Epic chart within 6 weeks postoperative.
- Each chart will be reviewed and the following data will be collected or extrapolated:
  - General demographic data – Name, date of birth, age, race, weight, height, BMI, parity, tobacco use, medical comorbidities, date of surgery, surgery performed, date of discharge, intraoperative and postoperative

complications, type of anesthesia, intraoperative intravenous fluid administration, estimated blood loss, discharge medications, postoperative urine cultures, prescribed UTI treatment, duration of catheter use, and any postoperative complications or readmissions (fever, ileus, hematoma, transfusion)

- **Intervention or experimental aspect of the study**
  - No intervention will occur as part of this study.
  - There are no potential risks to the study population by any aspect of the study.
- **Statistical Analysis**
  - The primary outcome is the incidence of UTI in patients who were discharged home with an indwelling urinary catheter after pelvic floor gynecologic surgery. To compare the primary outcome between two groups with/without cranberry capsules, the odds ratio and corresponding confidence interval will be utilized. Descriptive statistics will be generated for demographic information such as age, race, BMI, Parity etc. The independent samples t-tests or Mann-Whitney U test will be employed for continuous variables and the Fisher's exact or Pearson Chi-square tests for categorical variables to test any significant difference between two groups. Logistic regression will be implemented to determine potential risk factors for postoperative UTI.

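### The UTI window appears to open at surgery while exposure and eligibility are set at discharge, so infections found before discharge would count as outcome events

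*Combined protocol and SAP*

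**What the plan says.** All the relevant text is in the Research Plan of the combined protocol and SAP.

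- **Outcome (Data Collection, dependent variables):** a UTI is either a culture-positive result or treatment given by a provider, "with documentation in the Epic chart within 6 weeks postoperative". The end of the window is given; its start is not.
- **Exposure (Data Collection, independent variables):** "cranberry juice capsules prescribed as part of discharge medication regimen".
- **Eligibility (Inclusion criteria):** "Required indwelling urinary catheterization upon discharge from the hospital postoperatively".
- **Exclusions:** four are listed, covering the need for prolonged catheterization, early reoperation, cranberry allergy and missed office visits. None concerns a UTI diagnosed or treated before discharge.
- **Data abstracted:** "date of surgery, surgery performed, date of discharge", and later in the same list "postoperative urine cultures, prescribed UTI treatment, duration of catheter use". The cultures are not limited to those taken after discharge. No dates are named for cultures or treatment.
- **Analysis:** "To compare the primary outcome between two groups with/without cranberry capsules, the odds ratio and corresponding confidence interval will be utilized". The Statistical Analysis paragraph describes the outcome as incidence among women sent home with a catheter. That fixes who is counted, not when counting starts.

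**The concern.** The study asks whether adding capsules to the discharge regimen reduced UTI. A woman enters the cohort, and becomes exposed or unexposed, when she leaves hospital. A UTI cultured or treated during the stay comes before that point and says nothing about the capsules, yet the outcome as worded would include it in either year.

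Two things are at stake. If the pre-discharge risk is the same in both years, these events add equal noise to each group and pull the odds ratio toward 1. If it differs between years, which cannot be ruled out in a before-and-after comparison, it moves the odds ratio even when capsules do nothing. The definition accepts any positive culture or any treatment and requires no symptoms, so a difference in inpatient culturing alone could create such a gap.

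Leaving the start of the window open also means that abstractors, who can see the year of surgery, would have to decide individual cases for themselves.

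**Working it through.** **Inputs from the documents**

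- Cited trial (Purpose of Study and Background): 19% vs 38%, odds ratio 0.38.
- Charts (Sample size): 400 surgeries a year over 12 months gives about 400 charts.
- Share discharged with a catheter (Background): 54% after reconstructive surgery, 25% after slings. Applied to all 400 charts, these give 216 and 100 women. With the similar group sizes the plan expects, that is 108 or 50 per group, before exclusions.

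**Assumptions, not in the documents**

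- A pre-discharge UTI risk q of 1%, 2% or 5%.
- 38% (2015) and 19% (2016) used as the post-discharge risks. The documents quote them as overall incidences from a randomized trial, not as post-discharge rates and not as this study's design effect.
- Two-sided alpha of 0.05. The plan states no alpha, power or target effect.

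**Step 1. Reproduce the cited odds ratio.** (0.19/0.81) / (0.38/0.62) = 0.383, which agrees with 0.38.

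**Step 2. Add pre-discharge events.** Observed risk = q + (1 − q) × p. For q = 2%:

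- 2016: 0.02 + 0.98 × 0.19 = 0.2062
- 2015: 0.02 + 0.98 × 0.38 = 0.3924
- Odds ratio: (0.2062/0.7938) / (0.3924/0.6076) = 0.402

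**Step 3. Power.** Power = Φ[(d − 1.96 × SE0)/SE1], where d is the risk difference, SE0 the pooled and SE1 the unpooled standard error. For q = 0 and 108 per group:

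- d = 0.19 and mean risk = 0.285
- SE0 = √(0.285 × 0.715 × 2/108) = 0.0614
- SE1 = √((0.38 × 0.62 + 0.19 × 0.81)/108) = 0.0601
- Power = Φ(1.16) = 88%

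| q in both years | Risk 2016 | Risk 2015 | Odds ratio | Power, 50 per group | Power, 108 per group |
|---|---|---|---|---|---|
| 0 | 0.190 | 0.380 | 0.383 | 56% | 88% |
| 1% | 0.198 | 0.386 | 0.393 | 54% | 87% |
| 2% | 0.206 | 0.392 | 0.402 | 53% | 85% |
| 5% | 0.231 | 0.411 | 0.429 | 49% | 82% |

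**Step 4. No capsule effect, but different q by year.** Take a post-discharge risk of 38% in both years.

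- q of 2% gives 0.02 + 0.98 × 0.38 = 0.3924. q of 5% gives 0.05 + 0.95 × 0.38 = 0.411.
- With 2% in 2016 and 5% in 2015, the odds ratio is (0.3924/0.6076) / (0.411/0.589) = 0.93. With the years reversed it is 1.08.
- With 1% and 3%, the same calculation gives 0.95 or 1.05.

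**The case against.** The strongest reply is that the effect is too small to matter. At 108 per group, a q of 1% to 2% is one or two women per group. The expected 95% confidence interval moves from 0.21–0.71 to 0.21–0.72 or 0.22–0.74. Even q = 5% shifts the log odds ratio by only ln(0.429/0.383)/0.30 ≈ 0.38 of a standard error. Among the cases in the table, only 5% at 50 per group takes the upper limit past 1, from 0.95 to 1.02. Nothing in the documents shows that any UTI will fall in this interval. Equal dilution is also conservative for the study hypothesis. All of this stands, and it limits the point to a modest improvement. It does not show that the definition is right: the correction does not depend on q, and the plan has no way of learning q unless it separates the two periods.

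A second reply is that the plan never says the window starts at surgery. That is correct. The start is the ordinary meaning of the word postoperative, not a written rule. But nothing in the plan would lead an abstractor to leave out an inpatient culture.

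A third is that re-anchoring leaves loose ends. This stands in part. The discharge date alone cannot classify an event, so event dates are needed. With the window still closing 6 weeks after surgery, time at risk after discharge varies slightly with length of stay.

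A reader might also infer more than the documents support:

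- **Immortal-time bias favouring cranberry.** Both groups pass through the same interval from surgery to discharge, and events in it would be counted in both.
- **A known change in inpatient culturing or length of stay between 2015 and 2016.** The documents report none; Step 4 is only a what-if.
- **Antibiotics for an inpatient UTI altering later risk at home.** The plan says nothing on this.

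**Conclusion.** The point holds as a mismatch in the primary outcome definition: counting appears to start at surgery, while exposure and eligibility are set at discharge. Followed as written, the plan would count events that a discharge prescription could not have prevented.

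The likely consequence is slight dilution. In the illustration, the odds ratio moves from 0.383 to at most 0.429 for q up to 5%, and power drops by up to 6 to 7 percentage points. A difference between years of 2% vs 5% would produce an odds ratio of 0.93 or 1.08 with no true effect. These figures rest on assumed pre-discharge risks and on borrowed outcome rates. They also rest on group sizes of 50 to 108, of which 108 is the favourable end.

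The documents do not support saying that the primary comparison is seriously biased or that pre-discharge UTIs are common. The change is worth making because it is cheap and matches the outcome to the question asked.

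**What to change.** - **Primary outcome:** the first UTI, by the plan's existing definition, dated after hospital discharge and within 6 weeks of surgery. The governing date is specimen collection, or treatment start if there is no culture. A culture taken before discharge and reported afterwards then counts as pre-discharge.
- **At-risk set:** exclude women with a UTI dated on or before discharge, by the same rule in both years, and report their number per year. The exclusion uses only information from before the capsules could act, and the counts show how large the problem was.
- **Abstraction form:** add specimen-collection date and treatment-start date next to the discharge date already listed.
- **Sensitivity analysis:** repeat the comparison with all UTIs from surgery to 6 weeks.

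The cost is a revised outcome definition, one exclusion rule, two date fields taken from chart entries that are being opened anyway, and the loss of probably a few women. Time at risk after discharge will still differ slightly with length of stay.

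### Operating surgeon is not a planned data field, so a change in operator mix between 2015 and 2016 could be mistaken for a cranberry effect, and the planned dataset could not show it unless charts were reopened.

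*Combined protocol and SAP*

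**What the plan says.** - **Who is eligible.** The Participants part of the Research Plan admits surgery "performed by a physician at Cincinnati Urogynecology Associates". The number of physicians is not given.
- **What is extracted.** The Data Collection list includes "date of surgery, surgery performed, date of discharge, intraoperative and postoperative" complications, then "type of anesthesia, intraoperative intravenous fluid administration, estimated blood loss, discharge medications, postoperative urine cultures, prescribed UTI treatment, duration of catheter use". Operating surgeon does not appear. Nor is it among the candidate risk factors in the Secondary Aim under Purpose of Study.
- **How exposure is defined.** The Sample size part labels the two six-month windows as "exposure (cranberry juice capsules, 2016) and no exposure (no cranberry juice capsules, 2015) groups".
- **How the outcome is defined.** A UTI is a documented positive urine culture or "treatment by an involved provider", recorded in the chart within six weeks of surgery.
- **How the groups are compared.** Under Statistical Analysis, "the odds ratio and corresponding confidence interval will be utilized" for the primary outcome. Logistic regression is assigned to the search for risk factors. Nothing says that it adjusts the cranberry comparison.

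**The concern.** In a comparison of one year with another, anything that changed between the years lines up with exposure. Operator mix deserves attention because a clinician who cultures or treats more readily records more UTIs at the same true infection rate. Discharge with a catheter (the entry criterion) and catheter duration (an outcome in the second hypothesis and a candidate risk factor in the Secondary Aim) may also vary with the operator's practice.

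If surgeons differ in these habits and their shares of the caseload changed from 2015 to 2016, part of the crude odds ratio would reflect who operated. The bias could run either way: it could imitate a benefit or hide one. The Background says a positive result would support keeping capsules in standard practice, so the reader needs some assurance on this point. The planned dataset offers none.

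**Working it through.** **1. The plan's own figures.** 400 surgeries a year over two six-month windows gives 400 × 12/12 = 400 charts, as stated. The cited trial's 19% versus 38% gives (0.19/0.81)/(0.38/0.62) = 0.383, matching the quoted 0.38. The plan states no alpha or power, and no figure for surgeon-specific rates or shares.

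**2. Assumptions for the illustration.** None of these is in the documents. There are two surgeon groups, with UTI rates of 20% and 40% under the study definition, and capsules have no effect. Let s be the low-rate group's share of cases in a year.

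- Rate in a year: p = s × 0.20 + (1 − s) × 0.40
- Spurious odds ratio: [p16/(1 − p16)] / [p15/(1 − p15)]

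**3. Results, starting from a 50/50 split in 2015.** p15 = 0.5 × 0.20 + 0.5 × 0.40 = 0.30.

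- 60/40 in 2016: p16 = 0.6 × 0.20 + 0.4 × 0.40 = 0.28; OR = (0.28/0.72)/(0.30/0.70) = 0.91.
- 70/30 in 2016: p16 = 0.7 × 0.20 + 0.3 × 0.40 = 0.26; OR = (0.26/0.74)/(0.30/0.70) = 0.82.
- 30/70 in 2016 (the reverse shift): p16 = 0.3 × 0.20 + 0.7 × 0.40 = 0.34; OR = (0.34/0.66)/(0.30/0.70) = 1.20, which would mask a benefit.
- Unchanged mix: p16 = p15, OR = 1, no bias.

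**4. Range over other assumptions.**

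| Rates in the two groups | Low-rate share, 2015 → 2016 | p15 → p16 | Spurious OR |
|---|---|---|---|
| 20%, 40% | 40% → 60% | 0.32 → 0.28 | 0.83 |
| 20%, 40% | 30% → 70% | 0.34 → 0.26 | 0.68 |
| 20%, 40% | 20% → 80% | 0.36 → 0.24 | 0.56 |
| 20%, 40% | 0% → 100% | 0.40 → 0.20 | 0.375 |
| 10%, 64% | 40% → 60% | 0.424 → 0.316 | 0.63 |
| 10%, 64% | 30% → 70% | 0.478 → 0.262 | 0.39 |

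The 10% and 64% are the ends of the incidence range in the Background. That range describes published results in general, not surgeons within one practice, so the last two rows are an outer limit.

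**5. Chance of a false significant benefit.** The Background gives 25% to 54% of patients discharged with a catheter, depending on procedure. Of about 200 operations per window, that is 50 to 108 women per group before exclusions. With two-sided alpha of 0.05 (assumed), the chance is Φ[(d − 1.96 × se0)/se1], where d is the difference in rates and se0 and se1 are its pooled and unpooled standard errors. At 50 to 108 per group:

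- OR 0.91: 4% to 5%
- OR 0.82: 6% to 10%
- OR 0.68: 14% to 25%
- OR 0.56: 26% to 49%

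With no bias, the chance in that direction is 2.5%.

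**The case against.** The strongest reply is that the bias is hypothetical. It needs surgeons to differ in UTI rate and their shares to change, and the documents show neither. The windows cover the same six months of consecutive years in one practice. Modest shifts give 0.91 or 0.82, well short of the cited 0.38; at rates of 20% and 40%, only a complete switch of operators gets there. This stands, and it limits the severity.

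The plan also extracts catheter duration, cultures and prescribed UTI treatment, so some of the routes by which a surgeon could influence the outcome can be tabulated by year. That is partly right, but the plan does not commit to these tables, and they would not show whose patients they were. The lack of any adjusted cranberry comparison is a wider problem, and surgeon is only one covariate within it. That is also correct.

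Three stronger readings are tempting, and the documents do not support them:

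- **Several hospitals contribute.** A reader might infer this from the Setting paragraph, but the sentence is "The retrospective chart review will be performed on TriHealth EPIC platform at one of the various clinical locations". It says where the charts are read, not where women had surgery.
- **The loss is permanent.** Patient name, date of birth and date of surgery are extracted, identifiers stay in the source documents, and the spreadsheet is kept for ten years. If the chart names the operator, as is usual, the field could be recovered later by reopening charts.
- **A change in mix would necessarily be read as a capsule effect.** It could be, under the two conditions above.

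**Conclusion.** The point holds as a conditional one. Surgeon is absent from the extraction list and from the risk factors, exposure coincides with calendar year, and the primary odds ratio is crude. A change in operator mix could therefore bias the result without being visible in the planned dataset.

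Under the assumed 20% and 40% rates, moderate shifts from an even split produce a spurious odds ratio of 0.91 to 0.82. Larger distortions need a large shift or very different surgeons, and a stable mix produces none. The conclusion rests on there being more than one surgeon, which is a reasonable inference but is not stated. Severity is minor to moderate: the design survives, but the primary result would be harder to interpret than it needs to be.

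**What to change.** - Add one coded field, operating surgeon, to the Data Collection list, and fill it during the single planned chart review. Add discharging hospital only if more than one contributes.
- Tabulate surgeon by year. If the mix is stable, or there is only one surgeon, the table settles the matter.
- Report the cranberry–UTI odds ratio stratified by surgeon (Mantel-Haenszel or conditional logistic regression) or adjusted for surgeon, beside the crude odds ratio, and say whether the two agree. Pool low-volume surgeons by a rule set before outcomes are examined.
- Use the same stratification when comparing catheter duration.

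The cost is one spreadsheet column, read from charts that are already open. Sparse strata may widen the interval slightly. A surgeon who operated in only one of the two windows contributes no within-surgeon comparison, so this cannot repair a complete turnover of staff. Nor does it remove other differences between 2015 and 2016, and the report should say so.

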**Purpose of Study**

- The incidence of urinary tract infection (UTI) in women undergoing pelvic floor gynecologic surgery is high, ranging from 10-64% (Falagas, Athanasiou, Iavazzo, Tokas, & Antsaklis, 2008). A recent randomized trial showed that cranberry juice capsules significantly reduced the incidence of UTI in patients undergoing elective gynecologic surgery (19% vs 38%; odds ratio 0.38 with confidence interval 0.19-0.79) (Foxman, Cronenwett, Spino, Berger, & Morgan, 2015).
- Cincinnati Urogynecology Associates, TriHealth Inc incorporated this clinical regimen into their standard practice in early 2016. Currently, all patients who undergo pelvic floor gynecologic surgery and are discharged from the hospital with an indwelling urinary catheter postoperatively are prescribed cranberry juice capsules to reduce the risk of UTI.
- The purpose of this study is to determine if the addition of cranberry juice capsules to our discharge medication regimen for patients discharged home with an indwelling urinary catheter following pelvic floor gynecology surgery reduced the incidence of UTI.
  - **Primary Aim:** To determine the incidence of UTI in patients who were discharged home with an indwelling urinary catheter following pelvic floor gynecologic surgery in those who were prescribed cranberry juice capsules compared to those who were not.
  - **Secondary Aim:** To determine potential risk factors for postoperative UTI, other than urinary catheter use, such as certain demographic and perioperative factors including the following:
    - Age, race, BMI, tobacco use, medical comorbidities, type of surgery performed, type of anesthesia, intraoperative intravenous fluid administration, estimated blood loss, and duration of catheter use.

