### Background

Urinary tract infections (UTI) continue to be one of the most common healthcare-associated infections encountered today (Magill et al., 2012). The majority of these healthcare-associated UTIs are attributed to the use of urinary catheters (Hooton et al., 2010). Unfortunately, urinary catheter use is often unavoidable—as in the setting of postoperative urinary retention (POUR). Generally speaking, POUR can be characterized by any impairment in bladder emptying following surgery (Geller, 2014). Previous research has illustrated that POUR is a particularly common issue following urogynecologic surgery, with incidence rates of 1.4-43% (Dorflinger & Monga, 2001; Hakvoort, Elberink, Vollebregt, Ploeg, & Emanuel, 2004; Partoll, 2002). This means that a substantial number of patients will be discharged from the hospital with urinary catheters, putting them at substantially increased risk of developing a postoperative UTI. From an internal review of previously completed studies, approximately 54% and 25% of patients are discharged with a catheter following pelvic reconstructive surgery and suburethral sling procedures, respectively (Crisp et al., 2016).

The incidence of UTI has been estimated to be 3-4% per year for women in the general population (Foxman, 2014). However, for women undergoing urogynecologic surgery, the incidence of UTI is significantly greater, ranging from 10-64% (Falagas et al., 2008). As alluded to above, this increased incidence is likely related to postoperative urinary catheter use. Other risk factors for postoperative UTI have been postulated including age, menopausal status, history of recurrent UTIs, duration of catheter use, and increased distance between the urethra and anus (Foxman et al., 2015; Sutkin et al., 2010).

Previously, there has been much focus on the use of antibiotics to reduce the incidence of UTI in patients with indwelling urinary catheters. According to the most recent Cochrane Review, there remains limited evidence to indicate that receiving prophylactic antibiotics reduces the rate of bacteriuria and other signs of infection in surgical patients who undergo bladder drainage for greater than 24 hours postoperatively (Lusardi, Lipp, & Shaw, 2013). More recently, the focus of UTI prevention has turned to cranberry capsules.

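### Antibiotic use is neither compared between 2015 and 2016 nor named as a covariate, so any change in it would pass into the crude cranberry odds ratio

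*Combined protocol and SAP*

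**What the plan says.** **Exposure.** Under Research Plan (Sample size), exposure is calendar period. The two six-month windows are meant to give a "similar number of patients in the exposure (cranberry juice capsules, 2016) and no exposure (no cranberry juice capsules, 2015) groups".

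**Primary analysis.** Under Statistical Analysis, for the two-group comparison "the odds ratio and corresponding confidence interval will be utilized". No covariate is named. The only model has a different purpose: "Logistic regression will be implemented to determine potential risk factors for postoperative UTI". No adjusted cranberry effect is specified.

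**Group comparison.** "Descriptive statistics will be generated for demographic information such as age, race, BMI, Parity etc", followed by standard two-group tests. Antibiotics are not among the examples.

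**Antibiotics.** The Background says: "Previously, there has been much focus on the use of antibiotics to reduce the incidence of UTI in patients with indwelling urinary catheters". It then reports, from a systematic review, that the evidence of benefit for prophylaxis in catheterised surgical patients is limited. The secondary aim's candidate risk factors run from age and race to "type of surgery performed, type of anesthesia, intraoperative intravenous fluid administration, estimated blood loss, and duration of catheter use"; antibiotics are not among them.

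**Data.** The chart list includes "estimated blood loss, discharge medications, postoperative urine cultures, prescribed UTI treatment, duration of catheter use". It has no item for antibiotics given perioperatively or at catheter removal.

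**Outcome.** A UTI is a documented positive urine culture or "treatment by an involved provider" within six weeks of surgery.

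**The concern.** Exposure is set by year, so any other prevention practice that shifted between the two windows is confounded with cranberry. Antibiotics are the obvious candidate because the protocol itself names them as the previous approach in these patients. The Hypothesis section takes the comparison patients to have been treated alike apart from the capsules, but no step checks this.

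The bias could run either way. If antibiotics protect and their use rose in 2016, cranberry would look better than it is; if their use fell, a real benefit would be hidden. A second, lesser route is the outcome definition. It does not say that the treatment counted must be for a UTI, so an abstractor could in principle count a preventive prescription as a case.

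The Background says that the result will inform whether the practice keeps prescribing the capsules, so an odds ratio that carries an unexamined antibiotic change could mislead that decision.

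**Working it through.** **1. Figures in the documents.** The cited randomized trial's rates, 19% vs 38%, give (0.19/0.81)/(0.38/0.62) = 0.383, which agrees with the stated 0.38. The plan expects about 400 charts over 12 months, so about 200 per six-month window. With 25% (sling) to 54% (reconstructive surgery) discharged with a catheter, that is 200 × 0.25 = 50 to 200 × 0.54 = 108 patients per group before exclusions.

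**2. Assumed inputs.** The documents give no antibiotic rate for either year and no antibiotic effect size. I assume:
- UTI risk without antibiotics of 38% (the no-cranberry rate in the cited trial);
- no cranberry effect;
- share on antibiotics q, different in each year;
- antibiotic risk ratio RR from 0.5 to 1.0, where 1.0 means no effect.

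**3. Formula.** Risk in a year = 0.38 × (1 − q + q × RR). Crude odds ratio = odds in 2016 / odds in 2015.

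Worked case, q from 20% to 40%, RR 0.5: 2015 risk = 0.38 × 0.90 = 0.342; 2016 risk = 0.38 × 0.80 = 0.304; odds ratio = (0.304/0.696)/(0.342/0.658) = 0.840.

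| RR | Use 20% to 40%: risks | OR | Use 10% to 50%: risks | OR |
|---|---|---|---|---|
| 0.5 | 0.342, 0.304 | 0.84 | 0.361, 0.285 | 0.71 |
| 0.7 | 0.357, 0.334 | 0.90 | 0.369, 0.323 | 0.82 |
| 0.9 | 0.372, 0.365 | 0.97 | 0.376, 0.361 | 0.94 |
| 1.0 | 0.380, 0.380 | 1.00 | 0.380, 0.380 | 1.00 |

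If use did not change, the odds ratio is 1.00 for any RR.

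**4. Opposite direction.** If use fell by the same amount, the odds ratio is the reciprocal. For 40% to 20% it is 1/0.840 = 1.19 (RR 0.5) or 1/0.904 = 1.11 (RR 0.7). For 50% to 10% it is 1/0.706 = 1.42 or 1/0.817 = 1.22.

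**5. Against sampling error.** Take 108 per group and a two-sided 5% test (assumed; the plan states no level). The chance of a significant false benefit is about Φ(d/SE − 1.96), where d is the risk difference and SE = √[(p₁(1 − p₁) + p₂(1 − p₂))/108].
- 20% to 40%, RR 0.5: d = 0.038, SE = 0.0636, chance about 9%.
- 20% to 40%, RR 0.7: d = 0.0228, SE = 0.0647, chance about 5%.
- 10% to 50%, RR 0.5: d = 0.076, SE = 0.0634, chance about 22%.

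The reference value is 2.5% in that direction.

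**6. Outcome-counting route.** Assume no antibiotic effect on true UTI, use of 20% then 40%, and a fraction m of recipients without UTI scored as cases. Counted risk = 0.38 + q × m × 0.62. With m = 10% the risks are 0.392 and 0.405, odds ratio 1.05. With m = 100%, an extreme bound, they are 0.504 and 0.628, odds ratio 1.66.

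**The case against.** The strongest objection is that nothing in the documents shows antibiotic use differed between the years. The Background describes capsules as an addition to an existing standard discharge regimen, and its only statement on antibiotic effect is that the evidence is limited. With stable use or no effect the bias is zero; with RR 0.9 the odds ratio moves only to 0.97 or 0.94. In a study this small, moderate scenarios would seldom produce a false significant result. All of this stands. It limits the expected size but does not supply the missing check.

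A reader might also infer more than the text allows:
- *That discharge medications serve only to identify capsule prescriptions.* The plan does not say so. They are listed under demographic data, the descriptive comparison is open-ended, and the secondary-aim list is given as examples. Antibiotics are not excluded; they are just not pre-specified.
- *That antibiotics are completely inseparable from cranberry.* That would require use to go from none to all, or the reverse. With partial overlap, adjustment is possible.
- *That preventive antibiotics will be counted as UTIs.* This is not the natural reading. The definition concerns UTI, and the data list separates prescribed UTI treatment from discharge medications. The point justifies a clarifying phrase, no more.

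Finally, antibiotics are one instance of a wider gap: the plan has no adjusted cranberry effect at all. That is correct, and adding antibiotics to the risk-factor list alone would not repair the primary comparison.

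**Conclusion.** The point holds in conditional form. What is certain from the text is that the primary comparison is by year and unadjusted, that no antibiotic variable is named in any analysis, and that discharge medications are collected and could supply one. What is not known is whether antibiotic use changed or how much it matters. The documents do not support a claim that the cranberry estimate is biased, or in which direction.

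Under the assumptions of 38% risk and no cranberry effect, the spurious odds ratio runs from 0.71 to 1.00 for the rises examined and from 1.00 to 1.42 for the same changes reversed. It is exactly 1.00 if use was stable or antibiotics have no effect. The miscounting route is secondary. The change is worth making because it is nearly free and replaces an unverified assumption of similar treatment with a table.

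**What to change.** 1. Derive one yes/no variable, antibiotic at discharge not for a diagnosed UTI, from the discharge medications already collected, and tabulate it by year.
2. Add it to the risk-factor model.
3. Beside the crude odds ratio, pre-specify a logistic-regression cranberry odds ratio adjusted for this variable and a few other collected baseline factors, for example age, BMI and type of surgery. Leave catheter duration out of this model, since the Hypothesis section treats it as something cranberry may change.
4. State in the outcome definition that treatment means treatment prescribed for a UTI, not prophylaxis.
5. Optionally abstract perioperative and catheter-removal antibiotics as two separate fields and report them by year. Catheter-removal antibiotics follow exposure and should not be adjusted for by default.

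**Cost.** The derived variable needs no new data collection; the optional fields add two items per chart. The adjusted model has one more term and slightly wider intervals with roughly 50 to 108 patients per group before exclusions. At the cited trial's rates that is about 50 × (0.38 + 0.19) = 28 to 108 × 0.57 = 62 events in total, so the covariate list must be short. If the table shows that nearly all patients in one year and almost none in the other had antibiotics, no model can separate the two, and the report should say so. Other differences between the years remain in any case and should be stated as a limitation.
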